The primary and key secondary endpoints (for the main and second estimands) will be analysed by means of a Cochran-Mantel-Haenszel (CMH) model adjusted by country, age (adolescents/adults), prior use of dupilumab (yes/no), and baseline severity of disease (IGA=3/IGA=4). The FAS will be the primary analysis set; if the model does not converge, country will be removed as an adjusting factor. The estimate of the adjusted common risk difference, with corresponding Mantel-Haenszel-Sato (Sato 1989)⁵⁸ adjusted 2-sided 95% CI and p-value will be presented. Additionally, the CMH adjusted odds ratio along with the 95% two-sided asymptotic CI will be presented.

For analyses using multiple imputation, the analysis will be conducted on the complete dataset, for each imputation separately. Modelled results will be combined using Rubin's rule (PROC MIANALYZE) for tabulation.

Sensitivity Analysis for the Primary and Key Secondary Efficacy Endpoints:

The following sensitivity analysis will also be conducted for the main and second estimands of the primary and key secondary efficacy endpoints, on the overall population:

Table 11. Sensitivity Analysis

Analysis Set	Modelling Method	Estimand and Data Handling
Sensitivity Analysis Conducted on Main and Second Estimands		
PPS	CMH model adjusted by country, and stratification factors used in the randomisation (age, previous use of dupilumab, and baseline severity of disease, as per primary analysis).	As per main and second estimands

Abbreviations: CMH = Cochran-Mantel-Haenszel; PPS = Per Protocol Set.

Additional subgroup analyses based on baseline characteristics will be presented as appropriate using forest plots.

All inferential analyses of the primary and key secondary efficacy endpoints, including multiple imputation approaches, will be conducted during the Induction Period only (eg, up to and including Week 16). During the Maintenance Period, only descriptive analyses will be performed for efficacy. The handling of estimands as detailed above will also only apply up to and including Week 16. After this point, data will only be analysed as observed.

B. All Other Secondary and Other Efficacy Endpoints

All binary other secondary and other efficacy endpoints will be analysed using the same methodology as described above for the primary efficacy endpoint using only the main estimand. Sensitivity analyses based on the PPS population will not be conducted for these endpoints.

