7.5. Adjustments for Covariates

Unless otherwise specified, the statistical analysis models for the Induction Period efficacy and health outcome analysis will include the following stratification factors for Baseline randomization: age (adolescent patients 12 to <18 versus adults ≥18 years) and baseline disease severity (IGA=3 versus IGA=4). Additionally, the following factors will be included in the models:

- Country of patient as recorded at screening
- For analyses of the full population (i.e. not the subgroups of dupilumab naïve or previously exposed patients), the stratification factor of prior use of dupilumab (yes/no) will be included.

If the model does not converge, country will be removed as a factor from the specific model.

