9.3. Analysis of the Primary and Key Secondary Efficacy Endpoints

The primary and key secondary efficacy endpoints (for the main and second estimands) will be analysed by means of a Cochran-Mantel-Haenszel (CMH) model adjusted by country, age (adolescents/adults), prior use of dupilumab (yes/no), and Baseline severity of disease (IGA=3/IGA=4). If the model does not converge, country will be removed as an adjusting factor. The estimate of the adjusted common risk difference, with corresponding Mantel-Haenszel-Sato (Sato 1989) adjusted 2-sided 95% CI and p-value will be presented. Additionally, the CMH adjusted odds ratio along with the 95% two-sided asymptotic CI will be presented. The primary analysis will be based on the FAS which was defined as all randomized patients. When analysing the dupilumab naïve and previously exposed populations, the factor for prior use of dupilumab will be removed from the CMH adjustment.

Details are described in [Appendix 2](#). Details of Combining Estimates and Test Statistics for Categorical Endpoints with Multiple Imputation

Example code for CMH test:

CCI

This document is confidential.

For analyses using multiple imputation, the analysis will be conducted on the complete dataset, for each imputation separately. Modelled results will be combined using Rubin's rule (PROC MIANALYZE).

SAS Proc MIANALYZE will be used to combine the 100 point estimates (main estimand) for the difference in percentage of patients achieving EASI 75 response at Week 16 between treatments and standard errors, allowing appropriate statistical inference as described below:

CCI

The following sensitivity analysis will also be conducted for the main and second estimands of the primary and key secondary efficacy endpoints, on the overall population:

Analysis Set	Modelling Method	Estimand and Data Handling
Sensitivity Analysis Conducted on Main and Second Estimands		
PPS	CMH model adjusted by country, and stratification factors used in the randomisation (age, previous use of dupilumab, and Baseline severity of disease, as per primary analysis).	As per main and second estimands

Abbreviations: CMH = Cochran-Mantel-Haenszel; PPS = Per Protocol Set.

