Following the implementation of MCMC-MI imputation as specified in Section エラー! 参照元が見つかりません。, the data sets with imputations should be set together and sorted by imputation number. The following sections describe the processes for combining inferences for the individual imputed data sets into one inference for reporting. All calculations are performed in SAS software version 9.4 or higher.

Summarize Unadjusted Response Rate

The response rates, overall and by treatment arm, and their associated standard errors (SE) are computed for each imputed data set using PROC FREQ with the *riskdiff* option specified for the appropriate column in the TABLES statement. The response rates and SEs from the resulting output are combined across the imputed data sets using PROC MIANALYZE, separately for each arm and the overall group.

Note that the estimate and 95% confidence interval (CI) bounds output by PROC MIANALYZE are percents (i.e., they are in terms of the response rate). To obtain the number of responders, the estimated percentage is multiplied by the number of individuals in the analysis population and rounded to the nearest integer.

Compute Stratified Measures of Association

The common risk difference, common odds ratio (OR), and Cochran-Mantel-Haenszel (CMH) test statistic are computed for each imputed data set using PROC FREQ with the *riskdiff* option for the appropriate column (for risk difference) and the *cmh* option (for odds ratio and CMH test statistic) specified in the TABLES statement. Each of these analyses are stratified by geographic region, age group, and baseline disease severity via inclusion of these variables in the TABLES statement with the treatment and outcome variables.

Note that the PROC FREQ output corresponding to the Mantel-Haenszel method is used for the risk difference, and the output corresponding to the General Association statistic is used for the CMH statistic. PROC MIANALYZE is then called separately for each of these measures, with further details in the sections below.

Common Risk Difference

No transformation is necessary before using PROC MIANALYZE to combine the risk difference estimates and their associated SEs across the imputed data sets. This procedure outputs an estimate of the common risk difference and the associated 95% CI bounds.

Common Odds Ratio

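### SAP Appendix 2 stratifies the multiply imputed primary analysis by a different factor list from SAP 9.3, SAP 7.5 and the protocol

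*SAP*

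**What the plan says.** SAP 9.3 analyses the primary and key secondary endpoints with a CMH model "adjusted by country, age (adolescents/adults), prior use of dupilumab (yes/no), and Baseline severity of disease (IGA=3/IGA=4"). It then sends the reader to Appendix 2, headed "Details of Combining Estimates and Test Statistics for Categorical Endpoints with Multiple Imputation".

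Protocol 11.8.1.1 has the same four factors, "adjusted by country, age (adolescents/adults), prior use of dupilumab (yes/no), and baseline severity of disease (IGA=3/IGA=4"), and so does the protocol synopsis. SAP 7.5 names age and baseline severity, adds country, and for the full population says that "the stratification factor of prior use of dupilumab (yes/no) will be included". The per-protocol sensitivity table in SAP 9.3 uses country plus the "stratification factors used in the randomisation (age, previous use of dupilumab, and Baseline severity of disease, as per primary analysis").

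SAP 9.3 allows two departures. In the dupilumab-naive and previously exposed subgroups, "the factor for prior use of dupilumab will be removed from the CMH adjustment". Otherwise, "If the model does not converge, country will be removed as an adjusting factor".

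Appendix 2, under Compute Stratified Measures of Association, covers the common risk difference, the common odds ratio and the CMH statistic in every imputed data set. There the text is: "Each of these analyses are stratified by geographic region, age group, and baseline disease severity".

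**The concern.** SAP 9.1 limits confirmatory testing to the main estimand of EASI 75 at Week 16, and SAP 7.9 makes study success depend on that endpoint alone. SAP 6.3 and 6.3.1 handle that estimand by multiple imputation. Appendix 2 is therefore the text that tells a programmer how to compute the one confirmatory result.

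Followed literally, it gives a different analysis from the one stated elsewhere, with a different estimate, confidence interval and p-value. It would also make the sensitivity table wrong where it says that its factors match the primary analysis. A programmer following Appendix 2 would have to invent the regions. The protocol lists region among baseline characteristics without categories (synopsis and 11.6), SAP 8.3 does not list it, and all the planned countries are in Europe.

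The visible text states no precedence between 9.3 and Appendix 2. Protocol 11.2 lets the SAP override the protocol, so the protocol cannot formally decide a conflict inside the SAP. The example CMH code in 9.3 is redacted. That is no fault of the plan, but it means the code cannot answer the question here.

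**Working it through.** **1. Factor lists side by side.**

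| Place | Country | Region | Age group | Prior dupilumab | Baseline IGA |
|---|---|---|---|---|---|
| Randomisation (Protocol 9.6.2, SAP 4.1.2) | no | no | yes | yes | yes |
| Protocol synopsis and 11.8.1.1 | yes | no | yes | yes | yes |
| SAP 7.5 | yes | no | yes | yes | yes |
| SAP 9.3, main text and sensitivity table | yes | no | yes | yes | yes |
| SAP Appendix 2 | no | yes | yes | no | yes |

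Only age and baseline severity are common to 9.3 and Appendix 2.

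**2. Readings that might reconcile them.**
- *Region means country.* Prior dupilumab is still missing.
- *Appendix 2 is meant for the dupilumab subgroups.* Its text has no such limit, 9.3 cites it for the primary analysis, and country would still have become region.
- *Appendix 2 is the non-convergence fallback.* That rule removes country. It does not drop dupilumab or add region.
- *A deliberate change.* SAP section 11 lists the changes from the protocol and mentions none to these factors.

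**3. Number of strata.** With about 9 countries (protocol synopsis), the 9.3 list gives 9 x 2 x 2 x 2 = 72 possible strata, or 312/72 = 4.3 patients each. Without country there are 8. Appendix 2 gives 4R strata for R regions: 8 if R = 2, 12 if R = 3, and 36 if region is read as country.

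**4. The plan's power figure.** Inputs from SAP 4.3: 208 v 104 patients, two-sided 5%, EASI 75 55% v 30%.
- Pooled rate = (104 x 0.30 + 208 x 0.55)/312 = 0.4667.
- SE under the null = sqrt(0.4667 x 0.5333 x (1/104 + 1/208)) = 0.0599.
- SE under the alternative = sqrt(0.30 x 0.70/104 + 0.55 x 0.45/208) = 0.0566.
- z = (0.25 - 1.96 x 0.0599)/0.0566 = 2.34, so power is 99.0%.

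The stated figure of more than 95% is reproduced. The same formula gives 96.1% for IGA 0/1 (30% v 12%) and above 99.9% for pruritus (43% v 9%). The product is 95.2%, in line with the stated overall power of more than 90%. These calculations are unstratified, so they do not depend on the factor list.

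**5. How often the lists would give different answers.** The documents do not give country or prognostic effects, so this step rests on assumptions:
- 312 patients, 39 of them adolescents (12.5%), and 15, 30 or 60 dupilumab-exposed (60 is the cap in Protocol 7.1).
- 2:1 blocks of six within the randomisation strata.
- Nine countries, equal or skewed from 22% to 4%, with a between-country SD of 5 points.
- IGA 4 share 30-60%; effects of IGA 4 and of prior dupilumab on response 0-20 points.
- Region read as two groups of countries, three groups, or country itself.

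Both lists were applied to the same data, using the Mantel-Haenszel risk difference with Sato variance and the CMH test. There were 4000 replicates per scenario, for a Monte Carlo SE of about 0.2 points. At 55% v 30%:

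| Quantity | Two or three regions | Region = country |
|---|---|---|
| Disagreement on p<0.05 | 1.2-1.9% | 0.6-1.2% |
| Median gap in risk difference (points) | 1.3-1.7 | 0.7-1.1 |

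Power was 97.4-98.3% under the 9.3 list and 98.0-99.4% under Appendix 2. Type I error was 4.2-5.4% under every list. A separately coded run with 2000 replicates gave disagreement of 1.2-1.7% (two regions) and 0.5-1.0% (country). With 10% missing data and 100 imputations the ranges were 1.4-2.2% and 0.8-1.9%. Those imputation runs pool the risk difference by Rubin's rules, not the transformed CMH statistic of Appendix 2.

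**The case against.** The strongest reply is that this is one stray sentence. The protocol, its synopsis, SAP 7.5, SAP 9.3 and the sensitivity table all agree, and section 11 is silent because nothing was meant to change. At the planned effect the choice would rarely alter the conclusion. All of that stands, and it limits the importance of the point. It does not remove the contradiction, because the stray sentence sits in the text that specifies the computation.

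A reader might also infer that the country fallback should go, since Mantel-Haenszel and CMH statistics are closed-form and cannot fail to converge. That is true of iteration, but the conclusion does not follow. SAP 9.5 and Protocol 11.8.1.2 repeat the analysis in the dupilumab-exposed subgroup, capped at 60 patients. With country kept, that means 9 x 2 x 2 = 36 strata. Simulation of that subgroup, with 12.5% adolescents, 40% IGA 4 and otherwise similar assumptions, gave for 15, 30 and 60 exposed patients:

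| Quantity | Country kept | Country removed |
|---|---|---|
| Patients in one-arm strata | 68-73%, 50-55%, 31-34% | about 9%, 4-5%, 1% |
| Odds ratio zero or undefined | 83-88%, 32-39%, 3% | 26-27%, 4%, 0.1% |

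Removing country is the only fallback in the plan for such sparse tables, so it should stay. The Cox paragraph in SAP 9.4 ties its own removal of country to the other efficacy analyses and needs no change on this account.

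**Conclusion.** The contradiction is confirmed from the text and should be corrected before unblinding. Appendix 2 replaces country with an undefined region, omits a randomisation factor, and is the cited detail for the confirmatory analysis. The weight of the documents favours the 9.3 list.

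The size is small. About 0.5-2% of simulated trials at the planned effect change sides of p = 0.05, and the risk difference typically moves by 1 to 2 points. These figures depend on the assumed country effects, prognostic effects, exposed numbers and region groupings; the documents alone do not fix them.

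A reader might infer that the primary test is invalid or underpowered. The check does not support that: type I error is about 5% and EASI 75 power exceeds 95% under both lists. Nor do the documents show a deliberate late change of the adjustment factors. Larger disagreement rates can be produced by assuming a smaller effect or by looking at IGA 0/1. The first is not the planned effect, and the second is not confirmatory under SAP 7.9 and 9.1.

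**What to change.** Replace the sentence in SAP Appendix 2 with: *stratified by country, age group, prior use of dupilumab and baseline disease severity (IGA 3/4), as in Section 9.3; prior use of dupilumab is omitted only in the dupilumab-naive and previously exposed subgroup analyses.* Leave the country-removal fallback in SAP 7.5 and 9.3 in place.

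The cost is one sentence in a SAP revision, with no change to data, design or sample size. Section 11 needs no entry, because the corrected text matches the protocol. The 9.3 list does bring a sparse table in the overall population: about 43-56 of the 72 cells are occupied in simulation, with 9-12% of patients in one-arm cells that carry no weight. The protocol already accepts that.

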Appendix 3. Definition of Rescue Medications

This appendix provides the definition of rescue medications for this study, including topical and systemic treatments defined as follows:

1. Topical Atopic Dermatitis Treatment (including topical corticosteroids, TCI, and crisaborole)

Route of topical treatments includes: Topical and Transdermal.

Topical Corticosteroids (TCS): ATC code is D07

High or Ultra High Potency TCS: as per eCRF classification

Topical calcineurin inhibitor (TCI): Preferred Term includes: TACROLIMUS, PIMECROLIMUS

Crisaborole: Preferred Term includes: CRISABOROLE

2. Systemic Atopic Dermatitis Treatment (including systemic corticosteroids, immunosuppressant, biologics and phototherapy/photochemotherapy)

Route of systemic treatments administration includes: Oral, Intra-Arterial, Intramuscular, Intraperitoneal, Intravenous, Subcutaneous, Transdermal. (This condition applies to the following categories except for phototherapies.)

Systemic Corticosteroids: ATC code is H02

Immunosuppressant: Defined as: ATC2 is L04 or Preferred terms of Abrocitinib or Ruxolitinib or Upadacitinib or Baricitinib

Biologics: Defined as following Preferred terms:

Infliximab, Infliximabum, Etanercept, Etanerceptum, Adalimumab, Adalimumabum, Certolizumab, Certolizumabum, Certolizumab pegol, Golimumab, Golimumabum, Ozoralizumab, Afelimomab, Afelimomabum, Tumor Necrosis Factor Alpha (TNF-) Inhibitors, Tabalumab, Tregalizumab, Anakinra, Basiliximab, Basiliximabum, Daclizumab, Daclizumabum, Tocilizumab, Tocilizumabum, Mepolizumab, Mepolizumabum, Rilonacept, Rilonaceptum, Ustekinumab, Canakinumab, Briakinumab, Fezakinumab, Sirukumab, Sarilumab, Lebrikizumab, Secukinumab, Olokizumab, Gevokizumab, Brodalumab, Ladarixin, Ixekizumab, Dupilumab, Tildrakizumab, Tildrakizumabum, Reslizumab, Reslizumabum, Guselkumab, Guselkumabum, Olamkicept, Fletikumab, Bimekizumab, Mirikizumab, Risankizumab, Abatacept, Ligelizumab, Vedolizumab, Belimumab, Nemolizumab, Tralokinumab, Omalizumab, Benralizumab

Phototherapy or Photochemotherapy:

This document is confidential.

Programming search of medication name (actual term or preferred term) contains 'photo' then medicals to manually review to confirm whether the medication in question is indeed 'Phototherapy' or 'Photochemotherapy'

This document is confidential.

SAP text Version: SAP text v2.0 22MAR2023
Controlled Document ID: **CCI** Effective Date 31-Aug-2020
Filing requirements: TMF

Page 73 of 73

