8.3 Exclusion Criteria

Patients fulfilling any of the following criteria are not eligible for inclusion in this trial:

1. Participation in a prior lebrikizumab clinical study

2. Treatment with IL-4 or IL-13 antagonists biological therapies before the Baseline visit. Exception: previous treatment with dupilumab will be allowed in a subset of patients (please see [Section 7.2.2](#) for the definition of this subpopulation). A washout of at least 8 weeks before the Baseline visit will be required for this subpopulation
3. Treatment with TCS within 1 week before the Baseline visit
4. Treatment with topical calcineurin inhibitors, phosphodiesterase-4 inhibitors such as crisaborole, or cannabinoids within 2 week before the Baseline visit
5. Treatment with any of the following agents within 4 weeks before the Baseline visit:
 - a. Immunosuppressive/immunomodulating drugs (eg, systemic corticosteroids, cyclosporine, mycophenolate-mofetil, interferon- γ , JAK inhibitors, azathioprine, methotrexate, etc.)
 - b. Phototherapy and photochemotherapy (PUVA) for AD
6. Treatment with the following before the Baseline visit:
 - a. An investigational drug within 8 weeks or within 5 half-lives (if known), whichever is longer;
 - b. B cell-depleting biologics, including but not limited to rituximab, within 6 months;
 - c. Other biologics within 16 weeks or 5 half-lives (if known), whichever is longer
7. Treatment with a live (attenuated) vaccine within 12 weeks of the Baseline visit, planned during the study, or 18 weeks after the study treatment is discontinued
8. History of anaphylaxis as defined by the Sampson criteria⁴⁷
9. Regular use (more than 2 visits per week) of a tanning booth/parlour within 4 weeks of the Screening visit
10. Uncontrolled chronic disease that might require bursts of oral corticosteroids, eg, co-morbid severe uncontrolled asthma (defined by an Asthma Control Questionnaire-5 score ≥ 1.5 or a history of ≥ 2 asthma exacerbations within the last 12 months requiring systemic [oral and/or parenteral] corticosteroid treatment or hospitalisation for > 24 hours)
11. Have had any of the following types of infection within 3 months of Screening or develop any of these infections before randomisation:
 - a. Serious (requiring hospitalisation, and/or IV or equivalent oral antibiotic treatment);
 - b. Opportunistic (as defined in Winthrop et al. 2015). NOTE: Herpes zoster is considered active and ongoing until all vesicles are dry and crusted over;

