9.9 Pre-trial, Concomitant, and Post-trial Medications/Therapy

9.9.1 Pre-trial Medications

To ensure proper washout and review of prohibited medications, any prohibited treatment or treatment requiring a washout period (as outlined in [Table 5](#), and [Section 9.9.2](#)) taken by patient before signing the ICF be recorded in the eCRF (in Previous and Concomitant Medication).

A complete concomitant AD therapy history and reason for discontinuation (if applicable) will be recorded in the eCRF.

Any medication taken for medical reasons (mainly diseases concomitant with studied disease) before trial entry, will be continued at the same dose and under the same conditions during the entire experimental phase of the trial. See [Section 8.3](#) and [Table 5](#) for background therapies that are not permitted in this trial.

Table 5. Prior Treatment Exclusions

Drug Class	Washout Period
IL-4 or IL-13 antagonists	N/A (not allowed) ^a
TCS	1 weeks
Topical calcineurin inhibitors	2 weeks
Phosphodiesterase-4 inhibitors (eg, crisaborole)	2 weeks
Cannabinoids	2 weeks
Immunosuppressive/immunomodulating drugs (eg, systemic corticosteroids, cyclosporine, mycophenolate-mofetil, IFN- γ , JAK inhibitors, azathioprine, methotrexate)	4 weeks
Phototherapy and photochemotherapy (PUVA)	4 weeks
Investigational drugs	8 weeks or 5 half-lives (if known), whichever is longer
B cell-depleting biologics, including but not limited to rituximab	6 months
Other biologics	16 weeks or 5 half-lives (if known), whichever is longer
Live (attenuated) vaccine	12 weeks

Abbreviations: IFN = interferon; IL = interleukin; JAK = Janus kinase; PUVA = psoralen and ultraviolet A; TCS = topical corticosteroids.

^aPrior treatment with dupilumab will be allowed in a subset of patients. A washout of at least 8 weeks before the Baseline visit will be required for this subpopulation.

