9.9.3 Prohibited Concomitant Medications

The introduction of medications or therapies for other medical conditions known to have an effect on AD are not permitted during the study. These may include but are not limited to the list of medication as outlined in [Table 5](#) and below:

- The use of systemic corticosteroids for the treatment of AD is prohibited and requires permanent discontinuation of the Investigational Product. If a systemic corticosteroid is used for the treatment of AEs (eg, worsening of existing condition, such as asthma exacerbation), it will be treated as rescue medication.

- Acute infections can be treated with systemic antibiotics, use of which must be recorded in the eCRF. However, chronic treatment with systemic antibiotics is not permitted.
- The use of a tanning booth/parlour is not permitted during the trial.
- Cannabinoid treatments for AD are prohibited.

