6.1. Primary Efficacy Analysis (Overall Population)

6.1.1. Primary and Key Secondary Efficacy Endpoints

The primary efficacy analysis will be based on the main estimand for the overall population (FAS). The objectives, variables and population-level summary measures for the main estimand for the primary efficacy endpoint and key secondary endpoints is provided in table below:

Objectives/Treatment Condition of Interest	Variable/Outcome Assessed	Population-Level Summary Measure
To evaluate the efficacy of lebrikizumab compared with placebo in patients not adequately controlled with cyclosporine or for whom cyclosporine is not medically advisable up to Week 16 (ie, at the end of the Induction Period).	Title: EASI 75, IGA(0/1) and 2pt improvement, 4pt improvement in Pruritus NRS Description: Patient achieving: EASI 75: $\geq 75\%$ reduction in EASI score from Baseline, IGA: IGA score of 0 or 1 with 2pt improvement from baseline, Pruritus NRS: 4pt improvement from baseline Time Frame: 16 weeks	Population: Adult and Adolescent Patients with Moderate-To-Severe AD that are not Adequately Controlled with Cyclosporine or for whom Cyclosporine is not Medically Advisable. Measure: Difference between treatments (lebrikizumab minus placebo) in proportion of patients achieving EASI 75, IGA criteria, pruritus NRS criteria at Week 16

Abbreviations: AD = atopic dermatitis; EASI = Eczema Area and Severity Index (score); IGA = Investigator Global Assessment; NRS = Numerical Rating Scale.

The following ICEs are envisioned during the study, to be considered up to and including the Week 16 assessment:

- ICE1: Patient prematurely discontinues study treatment due to reasons other than lack of efficacy prior to Week 16.
- ICE2: Patient prematurely discontinues study treatment due to lack of efficacy prior to Week 16.
- ICE3: Patient receives rescue medication prior to Week 16 (either allowed or prohibited) for treatment of AD

Treatment discontinuation due to pandemic will be treated under the same intercurrent event as treatment discontinuation due to reasons other than lack of efficacy. Intermittent missing assessment due to pandemic and/or related restrictions will be treated the same as any other intermittent missing values. Details of how missing data will be handled for efficacy are described in [Section 6.3](#).

For supportive analyses a second estimand will be used.

This document is confidential.

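### ICE3 covers prohibited medication for AD, but SAP Appendix 3, the SAP's only coded definition of rescue medication, has no entry for cannabinoids, which the protocol prohibits for AD

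*SAP*

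**What the plan says.** **The event.** SAP Section 6.1.1 gives "ICE3: Patient receives rescue medication prior to Week 16 (either allowed or prohibited) for treatment of AD". The strategy table in the same section labels the event as rescue or prohibited drugs for AD. Under the main estimand the patient is set to the baseline value, and under the second to non-responder. Protocol Section 11.8.1.1 defines the same event and points to protocol Section 9.9.

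**The prohibition.** Protocol Section 9.9.3 states "Cannabinoid treatments for AD are prohibited". Before pregnancy, infection or other topics arise, eligibility already treats the class the same way: exclusion criterion 4 in Section 8.3 reads "Treatment with topical calcineurin inhibitors, phosphodiesterase-4 inhibitors such as crisaborole, or cannabinoids within 2 week before the Baseline visit", and Table 5 repeats these classes with a 2-week washout.

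**The code list.** SAP Appendix 3 opens with "This appendix provides the definition of rescue medications for this study, including topical and systemic treatments defined as follows". Its topical part ("Topical Atopic Dermatitis Treatment (including topical corticosteroids, TCI, and crisaborole") has lines for topical corticosteroids (TCS; ATC D07, with high or ultra-high potency taken from the eCRF), two calcineurin inhibitors, and "Crisaborole: Preferred Term includes: CRISABOROLE". Its systemic part has corticosteroids (ATC H02), immunosuppressants (ATC L04 plus four named JAK inhibitors), a list of named biologics, and phototherapy found by text search with manual medical review.

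**The concern.** The main estimand asks about responses at Week 16 reached without rescue medication, and ICE3 is the device that enforces this. For the flag to do its work, the coding rule must reach every AD treatment that the definition counts, prohibited ones included. Appendix 3 already goes beyond permitted rescue, since it lists calcineurin inhibitors, crisaborole, immunosuppressants and biologics. Yet it has no line for the one non-steroid AD treatment that Section 9.9.3 forbids by name.

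At stake is classification in the full analysis set. A patient who treats AD with a cannabinoid, stays on study drug and reaches EASI 75 could be counted as a response without rescue. The summary of intercurrent events planned in SAP Section 9.3 would then be short by that patient.

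**Working it through.** **1. Coverage, class by class**

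| AD treatment | Protocol | SAP Appendix 3 |
|---|---|---|
| High-potency TCS | rescue, 9.9.4 | D07, potency per eCRF |
| Systemic corticosteroids | prohibited 9.9.3, rescue 9.9.4 | H02 |
| Phototherapy | rescue, 9.9.4 | text search plus manual review |
| Calcineurin inhibitors | criterion 4, Table 5 | two preferred terms |
| PDE-4 inhibitors | criterion 4, Table 5 (class) | crisaborole |
| Cannabinoids | criterion 4, Table 5, and prohibited for AD in 9.9.3 | no entry |

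Only the last row is empty. No other section of the SAP gives codes for rescue or prohibited medication. Section 6.1.1 cites neither Appendix 3 nor protocol Section 9.9.3.

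**2. What happens to such a patient**

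- If the patient stops study drug, ICE1 or ICE2 applies and no observed Week 16 response is kept. Protocol Sections 8.3.2 and 9.9.4 require discontinuation for systemic rescue.
- Withdrawal for a serious violation (Section 8.3.1) is permitted, not required. A topical user can therefore stay on drug.
- If that patient is not flagged, the observed Week 16 value stands under both estimands.

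**3. Scale**

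Inputs from SAP Section 4.3: 208 lebrikizumab and 104 placebo patients, EASI 75 rates of 55% and 30%, two-sided 5%.

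The plan's own figure comes first, by the pooled-variance normal approximation:

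- pooled rate = (208 × 0.55 + 104 × 0.30)/312 = 0.4667
- SE under the null = √[0.4667 × 0.5333 × (1/104 + 1/208)] = 0.0599
- SE under the alternative = √[0.30 × 0.70/104 + 0.55 × 0.45/208] = 0.0566
- power = Φ[(0.25 − 1.96 × 0.0599)/0.0566] = Φ(2.34) = 99.0%, which agrees with the stated figure of more than 95%

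One unflagged EASI 75 responder who should have been set to baseline:

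| Arm of that patient | Shift in arm rate | Difference of 25 becomes | Power at those rates |
|---|---|---|---|
| Placebo | 1/104 = 0.96 points | 55 − 30.96 = 24.04 | 98.5% |
| Lebrikizumab | 1/208 = 0.48 points | 55.48 − 30 = 25.48 | 99.2% |

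The documents give no frequency of use. Purely as an assumption, 1 to 5 such patients all in one arm would shift the difference by 1.0 to 4.8 points (placebo, 5/104 = 4.8) or 0.5 to 2.4 points (lebrikizumab, 5/208 = 2.4). If they fell in the 2:1 ratio, the shifts would cancel (2/208 = 1/104).

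**The case against.** **Appendix 3 may not be the ICE3 list.** Its title speaks of rescue only, Section 6.1.1 does not cite it, and the protocol ties ICE3 to Section 9.9, which names cannabinoids. It also cannot run literally as a flag. The D07 line has no potency limit, although all patients must use low- or mid-potency TCS to Week 16. Nor does it carry a condition on date or on AD indication. Some further rule or clinical reading must be applied. This stands, and it is why the claim is that a user may not be flagged. A reader might infer that such a patient would certainly be missed, but the documents do not show that. The objection does not remove the gap: if Appendix 3 is not the list, the SAP has none, and manual review is written in for phototherapy alone.

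**The blinded data review will catch it.** Medications are recorded with indication (protocol Section 9.9.2) and tabulated (SAP Section 8.6.2). Deviations affecting primary efficacy are closed before database lock (SAP Section 5.4), and the per-protocol analysis repeats both estimands. These are real safeguards. But Sections 5.3 and 5.4 cover deviations, per-protocol exclusions and data handling issues. Neither says that the review sets ICE3 flags in the full analysis set, and a per-protocol exclusion does not change the primary estimate.

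**PDE-4 inhibitors.** A reader might infer an equal gap here, because the protocol names a class ("Phosphodiesterase-4 inhibitors (eg, crisaborole" in Table 5) and Appendix 3 codes one drug. The documents do not support that:

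- Criterion 4 and Table 5 are pre-baseline washout rules.
- The on-study sentence that points to Table 5 ("The introduction of medications or therapies for other medical conditions known to have an effect on AD are not permitted during the study") concerns drugs for other conditions, whereas ICE3 concerns treatment of AD.
- The crisaborole line is worded as an inclusion, so it is not clearly closed.
- Crisaborole is the only PDE-4 inhibitor that the documents name.

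**Conclusion.** The omission is real and minor. ICE3 counts prohibited AD medication, the protocol prohibits cannabinoids for AD by name, and the SAP's only coded definition of rescue medication has no line that captures them. A user who stays on study drug may keep an observed Week 16 response under both estimands, against the question that the main estimand asks.

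This rests on reading Appendix 3 as the working source for ICE3. That is an inference from its stated purpose and from the absence of any other code list. Each affected responder is worth 0.96 points (placebo) or 0.48 points (lebrikizumab). The effect is probably very small, because harm needs a patient who breaks the prohibition, stays on drug and responds. A reader might infer a bias towards lebrikizumab. The documents give no arm-specific use, so the direction is unknown. The stated power is not in question.

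**What to change.** Before unblinding:

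1. Add a line to SAP Appendix 3 for cannabinoids used to treat AD, whether topical or systemic.
2. In SAP Section 6.1.1, cite Appendix 3 and protocol Section 9.9.3 from the ICE3 definition.
3. Have the planned blinded data review read the on-study medications recorded with an AD indication and confirm the ICE3 flags.

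Optionally, word the crisaborole line as PDE-4 inhibitors with crisaborole as the example, to match exclusion criterion 4 and Table 5. This is a tidy-up, not a correction.

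The cost is one added line, one cross-reference and one short blinded listing review. No new data are needed, since indication is already collected. Done before unblinding, the change cannot be influenced by treatment results.
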